2.3. CALCULATION CONVENTIONS

2.3.1. Convention for defining follow-up time

- Follow-up during the run-period is defined as the amount of participation time for each participant enrolled from moment of inclusion (following sign inform consent) until the moment of randomisation
- Follow-up during the intervention period is defined as the amount of participation time for each participant enrolled from moment of randomisation until last study visit

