7.1.2 Secondary study parameters/endpoints

1. Incidence rate of HCV reinfection (number of cases of HCV reinfection divided by total person-years of follow-up at risk for reinfection) (self-reported and laboratory data).
2. Incidence rate of any STI (number of cases of chlamydia, gonorrhoea, lymphogranuloma venereum (LGV), genital herpes and/or syphilis divided by total person-years) (self-reported).
3. Changes in HCV-related risk behaviour:
 - a. Changes in the number of sex partners.
 - b. Changes in the number of condomless anal sex acts with casual partners.
 - c. Changes in the individual items of the HCV-MOSAIC risk score:
 - i. Changes in the proportion of individuals reporting receptive condomless anal sex.
 - ii. Changes in the proportion of individuals sharing sex toys.
 - iii. Changes in the proportion of individuals reporting unprotected fisting.
 - iv. Changes in the proportion of individuals reporting injection drug use.

- v. Changes in the proportion of individuals sharing snoring equipment during nasally-administered drug use.
- vi. Changes in the proportion of individuals reporting ulcerative sexually transmitted infection (syphilis, genital herpes or lymphogranuloma venereum infection).
- d. Proportion of individuals with change in any of the items of the HCV-MOSAIC risk score.
- e. Changes in the frequency of recreational drug use before and during sex.
- f. Changes in the frequency of individuals engaging in group sex activities, including changes in number of events and maximum number of sex partners during an event.
- g. Changes in the proportion of individuals sharing lubricants.
- h. Changes in the proportion of individuals sharing anal douches.

4. Changes in the proportion of individuals disinfecting sex toys, skin and/or sex location.
5. Changes in the sexual wellbeing score.

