7.3 Study procedures

Questionnaires

After the eligibility check and obtaining informed consent, participants will receive a login code and a link to the study website by email. All questionnaires will be offered online using email notifications or text notifications. After enrolment, participants will be invited to fill out the baseline questionnaire (i.e., at month 0). Subsequently, a questionnaire will be offered to all participants every 6 months (i.e., at month 6, 12, 18 and 24), measuring risk behaviour over the past 6 months. Email reminders will be sent to the participants in case the questionnaire was not completed 1.5 week and 3 weeks after the first email notification was sent.

Run-in period

All participants will receive standard care during the run-in period of six months. HIV-positive MSM will receive standard care during biannual visits at their HIV treatment center, where routine blood testing, including liver enzymes, takes place every 6 months according to national guidelines.(64) Testing policies for HCV reinfection might differ per HIV treatment center; some centers might perform annual testing and others might only test for HCV RNA in the presence of elevated liver enzymes. In addition, the majority of HIV-positive MSM regularly visits the STI outpatient clinic of a Public Health Service for STI testing.

Standard care among HIV-negative MSM differs. HIV-negative MSM using PrEP will usually receive STI testing at an STI/PrEP/sexual health center. MSM participating in the PrEP projects will routinely visit the STI clinic of the Public Health Service of Amsterdam for PrEP monitoring including STI screening (syphilis, hepatitis B, hepatitis C, HIV, chlamydia and gonorrhoea). MSM enrolled in the PrEP projects at the Public Health Service of Amsterdam are currently being tested for HCV reinfection every 3 to 6 months. HIV-negative MSM not using PrEP are not routinely tested for HCV infection, unless they are notified by a HCV positive sex partner.

Intervention period

After randomization at month 6, participants will be referred to one of the three arms on the study website: (1) the behavioural intervention (see **Chapter 5.1**), (2) the testing intervention (see **Chapter 5.2**), or (3) the combined intervention (see **Chapter 5.3**). In addition to standard care as described above, participants will be offered the intervention(s) for 18 months (month 6-24).

After the end of the study

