2.1.2. Secondary endpoints

- **Definition**

Secondary endpoints are as follows:

- Incidence rate of HCV reinfections during both the run-in (i.e., M0 and M6) and intervention period (i.e., M12, M18, M24), both self-reported and laboratory-confirmed, defined as the number of cases divided by the total person-years of follow-up at risk for reinfection
- Incidence rate of any STI during the run-in and intervention period, both self-reported and laboratory-confirmed, defined as the number of chlamydia, gonorrhoea, genital herpes and/or syphilis infections divided by the total person-years of follow-up
- Other HCV-related risk behaviour during run-in versus intervention period, more specifically:
 - Changes in the mean or median number of sex partners (depending on the distribution of the variable of interest)
 - Changes in the mean or median number of condomless anal sex acts with casual partners (depending on the distribution of the variable of interest)
 - Changes in the proportion of participants reporting any individual behaviours that are included in the HCV-MOSAIC risk score
 - Changes in mean or median sexual wellbeing score (depending on the distribution of the variable of interest)
- The proportion of participants achieving an HCV-MOSAIC risk score ≥ 2.0 at the end of follow-up compared between intervention arms (in both ITT and PP populations)

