3.3.2. Clinical characteristics at enrolment (M0) and during follow-up (M6 to M24)

- HCV-related clinical characteristics
 - Previous HCV infections (in counts)
 - Previous HCV treatment (yes/no)
 - HCV genotype
 - Time since first anti-HCV positive test (in years)
- HIV or pre-exposure prophylaxis (PrEP)-related clinical characteristics
 - HIV-status (positive or negative)
 - PrEP-use (yes/no)
 - Type of PrEP regimen (daily or event-driven)
- STI testing and testing outcomes (positive or negative), including chlamydia, gonorrhoea, genital herpes and/or syphilis (self-reported)

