3.5.2. Incidence rate of STI (chlamydia, gonorrhoea, genital herpes and/or syphilis)

- **Definition**

See paragraph 2.1.2.

Number of chlamydia, gonorrhoea, genital herpes and/or syphilis infections divided by the total person-years of follow-up is calculated.

- **Handling of missing data**

Analysis is performed in available data.

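### STI person-time includes questionnaire windows that were skipped, so intermittent non-response understates the intervention-period STI rate

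*SAP*

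**What the plan says.** **Rate.** SAP 2.1.2 gives the STI endpoint as "defined as the number of chlamydia, gonorrhoea, genital herpes and/or syphilis infections divided by the total person-years of follow-up". SAP 2.2.2 compares the two periods by Poisson regression with log person-years as the offset, overall and by arm.

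**Time.** SAP 2.3.1 takes intervention follow-up as "participation time for each participant enrolled from moment of randomisation until last study visit", with no deduction for gaps. Run-in follow-up goes from inclusion to randomisation.

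**Ascertainment.** Protocol 7.3 says that "a questionnaire will be offered to all participants every 6 months (i.e., at month 6, 12, 18 and 24), measuring risk behaviour over the past" six months. After the consent visit everything is done online or at home (SAP 3.1), so a study visit is in practice a questionnaire.

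**Missing data.** SAP 3.5.2 says only: "Analysis is performed in available data". HCV reinfection has its own time-at-risk rule, tied to RNA test dates (SAP 2.3.2). STI has none.

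**Case source.** The documents disagree. SAP 2.1.2 has "Incidence rate of any STI during the run-in and intervention period, both self-reported and laboratory-confirmed". Protocol 7.1.2 has "Incidence rate of any STI (number of cases of chlamydia, gonorrhoea, lymphogranuloma venereum (LGV), genital herpes and/or syphilis divided by total person-years) (self-reported" only, and SAP 3.3.2 lists STI outcomes "including chlamydia, gonorrhoea, genital herpes and/or syphilis (self-reported" only. SAP 2.3.2 also treats STI results as self-reported. Protocol 11.1 mentions linking STI data by name and date of birth, but under the collection of HCV reinfection data, and does not say which STIs or which participants are covered.

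**The concern.** The numerator can only receive self-reported infections from windows that a completed questionnaire covers, while the denominator is a continuous span. A skipped M12 or M18 followed by a later answer therefore enters the rate as six infection-free months. Restricting the analysis to available data limits the cases and leaves the time untouched.

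Such gaps are foreseeable. The sample-size target in SAP 1.4 asks for only one completed questionnaire in the intervention period, follow-up is remote with two reminders (protocol 7.3), and there are no incentives (protocol 10.5).

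The STI comparison is run-in against intervention, with no untreated arm, so randomisation does not cancel the error. The run-in is a single window closed by M6. Among month-6 completers it cannot contain a skipped window followed by a later visit; the three intervention windows can. An artefact in that direction would look like a benefit. In the analyses by arm, it would be larger in an arm with more intermittent gaps.

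**Working it through.** The documents give no STI rate, missed-questionnaire rate or STI power, so there is no figure of the plan's own to reproduce. The check compares covered time with counted time.

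**Inputs from the documents:** 18 months of intervention, as three 6-month windows ending at M12, M18 and M24 (SAP 1.2.1); counted time runs from randomisation to the last study visit (SAP 2.3.1), read here as the last completed questionnaire; 78 participants per arm (SAP 1.4).

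**Assumptions:** constant STI rate, cases from questionnaires only, on-time completion.

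**Step 1: one participant.** Factor = (6 months × questionnaires completed) / (months to the last completed one).

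| Missed | Covered / counted (months) | Factor |
|---|---|---|
| none | 18/18 | 1.00 |
| M24 only | 12/12 | 1.00 |
| M18 and M24 | 6/6 | 1.00 |
| M12 only, or M18 only | 12/18 | 0.67 |
| M12 and M24 | 6/12 | 0.50 |
| M12 and M18 | 6/18 | 0.33 |

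Only a gap followed by a later answer takes the factor below 1.

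**Step 2: average over participants.** Let m be an assumed, independent probability of missing each questionnaire.

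- Covered years = 1.5(1 − m)
- Counted years = 1.5(1 − m) + 1.0·m(1 − m) + 0.5·m²(1 − m)
- Factor = covered / counted = 3 / (3 + 2m + m²)

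| m | Covered | Counted | Factor | Spurious reduction |
|---|---|---|---|---|
| 5% | 1.425 | 1.4737 | 0.967 | 3% |
| 10% | 1.350 | 1.4445 | 0.935 | 6-7% |
| 20% | 1.200 | 1.3760 | 0.872 | 13% |
| 30% | 1.050 | 1.2915 | 0.813 | 19% |

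With a fully observed run-in and no true effect, the expected intervention/run-in rate ratio equals the factor.

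**Step 3: one arm.** Assume that all 78 complete M24, 10% miss each of M12 and M18, and the true rate is 0.50 per person-year. Counted time = 78 × 1.5 = 117.0 person-years. Covered time = 117.0 × (1 − 0.2/3) = 109.2. Expected cases = 0.50 × 109.2 = 54.6. The rate under SAP 2.3.1 is 54.6/117.0 = 0.467; on covered time it is 54.6/109.2 = 0.500. The relative shortfall of 6.7% does not depend on the rate assumed.

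**Step 4: other readings.**
- Pure drop-out, with no later answer: factor 1.00.
- Laboratory data recover half of the missed cases at m = 10%: 1 − 0.5 × (1 − 0.935) = 0.967.
- Last study visit read as scheduled M24 for everyone: factor 1 − m, that is 0.90 at 10% and 0.80 at 20%. Drop-out then biases the rate too.

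**Step 5: matched person-time.** If only covered windows are counted, the factor is 1.00 for every completion pattern.

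**The case against.** A reader might infer that any missed questionnaire biases the rate. The documents do not support that: follow-up stops at the last visit, so missed final questionnaires remove time along with cases. The same 90/85/80% completion at M12, M18 and M24 could arise from pure drop-out, with no bias at all.

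A reader might also take skipped windows to be wholly unobserved. SAP 2.1.2 includes laboratory-confirmed STIs, so some cases could still be captured. This stands as a limit on size. It does not remove the point, because three other places say self-report and neither document explains how laboratory STI results would be obtained for all participants.

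A third tempting inference is that the bias must fall on the intervention side alone. Protocol 9.1 restricts the primary ITT and PP analyses to month-6 completers; protocol 9.2 and SAP 3.5.2 do not repeat this for STI. Late questionnaires also leave small gaps in either period: a late M6 and randomisation stretch run-in time beyond the six-month recall.

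SAP 2.2.2 describes the offset as observed person-years, so an analyst could exclude unobserved windows. But the only definition of follow-up time, in SAP 2.3.1, does not do so.

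Finally, the effect is modest against sampling error. At an assumed 0.50 per person-year, one arm would yield about 78 × 0.5 × 0.50 = 19.5 run-in and 117 × 0.50 = 58.5 intervention cases. The standard error of the log rate ratio is then √(1/19.5 + 1/58.5) = 0.26. The bias at a 10% miss rate, ln 0.935 = −0.07, is about a quarter of that. This is fair for a secondary endpoint in a study that calls itself a pilot, but the error is systematic and more participants would not reduce it.

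**Conclusion.** The point holds in a limited form. As written, the STI denominator is not matched to the windows in which self-reported STIs can be recorded. Intermittent non-response (M12 or M18 skipped, a later questionnaire answered) therefore biases the intervention-period rate downward. The bias favours the interventions if the STI analysis is limited to month-6 completers, which the plan states only for the primary analyses.

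The size cannot be fixed from the documents. The range runs from no bias under pure drop-out to the 19% reduction at an assumed 30% independent miss rate with questionnaire-only cases. It should not be read as a forecast, and laboratory ascertainment would shrink it. The conclusion also rests on reading the last study visit as the last completed questionnaire; reading it as scheduled M24 makes the problem larger. Because this is a secondary endpoint and the remedy is cheap, the SAP should be corrected before analysis, but the primary result is not affected.

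**What to change.** In SAP 2.3.1 and 3.5.2:

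- Count STI person-time, in both periods, only over windows with a completed questionnaire: for each one, the shorter of six months and the time since the previous questionnaire, cut at randomisation. Use this as the Poisson offset.
- Count in the numerator only cases arising in those windows. Shrinking the denominator while keeping laboratory cases from skipped windows would bias the rate upward.
- Reconcile the case source between SAP 2.1.2 and protocol 7.1.2, SAP 2.3.2 and SAP 3.3.2. If laboratory-confirmed STIs are used, add windows with documented laboratory linkage to both numerator and denominator.
- Define the last study visit as the last completed questionnaire.
- State whether the STI analysis is limited to month-6 completers.
- Do not count M0 reports as run-in cases. They refer to the six months before inclusion, while run-in time starts at inclusion; including them could set up to 12 months of cases against 6 months of time.

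The cost is SAP wording and a short derivation from questionnaire completion dates. Person-years fall slightly (117.0 to 109.2 in the one-arm illustration), so intervals widen a little.

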2.3.2. Convention for time calculations

- Time between two dates in months or years is estimated as the number of months between two dates by subtracting the later date to the earlier date
- Calculation of age in years at enrolment =
$$\frac{\text{date of enrollment} - \text{date of birth}}{365.25}$$
- Date of HCV reinfection is estimated using the mid-date between the last HCV-RNA negative and first HCV-RNA positive test result
- Calculated time at risk for HCV risk is defined as the amount of participation time for each participant enrolled from moment of inclusion until estimated date of HCV reinfection or the last recorded HCV-RNA negative test date

- STI period prevalence is estimated using the proportion of participants that have a positive STI test result (self-reported) at any study visit during the past 6 months

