5.2 Arm II: home-based testing intervention

The second arm will consist of an additional patient-initiated home-based HCV testing service. The service will offer 4 free-of-charge HCV RNA tests, which can be obtained via email. It involves home-based HCV testing using self-sampled dried blood spots (DBS) (i.e., home-collection testing involving a certified laboratory) that was developed, used for purchase, and evaluated via the NoMoreC project (www.nomorec.nl) as part of the MC free initiative, a collaboration of relevant stakeholders that aims to reduce the incidence of HCV infections among MSM in Amsterdam. This service allowed men at high risk for HCV infection to take control and test for the presence of HCV-RNA. The self-sampling DBS has been previously validated and shown to be effective (see **Chapter 6**).

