2.2.2. Comparative analysis

The primary endpoint is compared between the run-in period (i.e., at M0, M6) and at each time point during the intervention period (i.e., at M12, M18, M24) using a mixed-effect logistic regression model. In this model, each individual serves as their own control and between-individual differences at baseline are accounted for using a random-intercept. Odd ratios (OR) comparing the odds of run-in versus intervention time points, along with their 95% confidence intervals (CI), are estimated and stratified on study arm. These stratified analysis are performed by including an interaction term between arm and study time point (along with their individual covariate) in the model, while study time points are statistically tested within strata of the study arms. Comparisons between run-in and intervention time points are systematically conducted as follows:

- Unadjusted;
- Adjusted on the randomisation strata (country and, if sufficient numbers of individuals in each intervention arm are available, inclusion centre [3]);
- Adjusted on covariates that could potentially affect the evaluation of the primary outcome

Incidence rates of HCV reinfections and STIs are calculated during the run-in and interventions periods, separately. Considering that few HCV reinfections are likely to occur,

we intend to analyse the relative difference in incidence rates between periods using a Bayesian exponential survival regression model with non to weakly informative *a priori* distributions [4, 5]. The relative difference in incidence rates of STIs are compared between periods using a Poisson regression model with ln of person years of observation as an offset. These models are run on both the overall study population and stratified by treatment arm (using the same model configuration of fixed-effect covariates as in the primary endpoint).

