3.2. DESCRIPTION OF DEVIATIONS TO THE PROTOCOL

3.2.1. Eligibility criteria assessment

- Participants with unmet eligibility criteria (n, %) – the denominator of the proportion is the number of participants enrolled
- Unmet eligibility criterion per participant

Verification of eligibility criteria is performed by the treating physician and nurses of participating centres prior to participant enrolment using data collected in the medical file. All eligibility criteria (inclusion and exclusion) are listed in Table 1 below.

Table 1. Eligibility criteria assessed by the treating physician and nurses prior to participant enrolment

Inclusion criteria	Exclusion criteria

1. ≥18 years of age2. Previously cured or spontaneously cleared HCV infection (i.e., positive HCV RNA test and/or positive anti-HCV antibody in the past with currently negative HCV RNA)3. Self-reported MSM4. Attending care at an human immunodeficiency virus (HIV) treatment centre (for participants with HIV) or a Centre for Sexual Health (CSH) or Centres gratuits d'information, de dépistage et de diagnostic (CeGIDD) (for participants without HIV)5. Sufficient understanding of Dutch or English (for participants in the Netherlands) or French (for participants in France)6. Accept to be contacted by telephone	
1. Acute or chronic HCV infection2. Participation in another study offering an HCV testing and/or an intervention targeting behaviours associated with risk of acquiring3. Receiving HCV treatment4. Being under legal guardianship (for participants in France)5. Not able or incapable to provide informed consent6. Suspected non-compliance with study procedures

7. Have health coverage within the national healthcare system (for participants in France)
 
8. Have access to internet and an e-mail messaging service
	
7. Individuals who are investigators or otherwise dependent persons are also not included in the study

---	---

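### Mid-point dating of reinfections makes the run-in versus intervention rate ratio depend on each man's HCV-RNA testing schedule, which changes at month 6 in arms II and III

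*SAP*

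**What the plan says.** SAP 2.3.2 gives each reinfection a single date: "Date of HCV reinfection is estimated using the mid-date between the last HCV-RNA negative and first HCV-RNA positive test result". Time at risk runs "from moment of inclusion until estimated date of HCV reinfection or the last recorded HCV-RNA negative test date". SAP 2.3.1 ends the run-in at randomisation, counting it "from moment of inclusion (following sign inform consent) until the moment of randomisation". SAP 2.2.2 then compares the incidence rates of the two periods, overall and by arm, with a "Bayesian exponential survival regression model".

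On test timing, Protocol 7.3 says of the HIV treatment centres that "some centers might perform annual testing and others might only test for HCV RNA in the presence of elevated liver enzymes". Men in the Amsterdam PrEP projects are tested every 3 to 6 months. SAP 3.2.1 requires men to enter "with currently negative HCV RNA" but does not date that test. Protocol Table 1 lists one RNA test only, on a stored sample after the end of the study and only if none was done in the last six months. For arms II and III, Protocol 5.2 adds: "The service will offer 4 free-of-charge HCV RNA tests". These become available after month 6, are recommended for use between clinic visits, and are prompted by reminders at months 12 and 18.

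Neither document mentions interval censoring, a rule for test gaps that straddle month 6, or a sensitivity analysis on event dating.

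**The concern.** The imputed date, not the infection, decides the period in which an event is counted. Where the gap between tests spans month 6, the mid-point can fall on the wrong side, and whether it does so depends on when the man was tested. In arms II and III the testing pattern changes at month 6 by design; in arm I it does not. The estimated period ratio then mixes the effect of the intervention with the effect of the schedule, and the mixture can differ by arm. At stake are the reinfection results in each arm and any reading of those ratios side by side.

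**Working it through.** **The plan's own figures.** The documents give no event count or power for reinfection. The stated 78 per arm belongs to the primary endpoint: 60% versus 38%, two-sided 5%, two independent proportions, gives 80 per arm, and 78 gives 79.1% power. That agrees closely and supplies the arm size used here.

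**Inputs from the documents.** Run-in 6 months, intervention 18 months, 78 men per arm, the dating and time-at-risk rules above, and the testing patterns in Protocol 5.2 and 7.3. Protocol 1.3 suggests a range of rates:
- low: ten times 3.3 per 1,000 = 0.033 per person-year;
- high: one third within two years, −ln(2/3)/2 = 0.203 per person-year.

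**Assumptions.** A negative test at month 0, a test at month 24 for every man, the timing of kits and annual visits, no test error and no spontaneous clearance. The main illustration assumes 0.05 per person-year.

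**The rule in algebra.** With the last negative at month 0 and the first positive at month h, the mid-date is h/2. Every h below 12 goes to the run-in and every h above 12 to the intervention period, whenever infection occurred. At h = 12 the date falls on the boundary, and there is no tie rule.

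**By hand, no effect, first later test a kit at month 9.** Nine months of events are counted in six months of run-in and 15 months of events in 18 months of intervention: (15/18)/(9/6) = 0.56 instead of 1.

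**By hand, true ratio 0.5, annual test close to month 12.** With run-in hazard λ per month, events by month 12 are 6λ + 6(0.5λ) = 9λ. If half the men test just before month 12 and half just after, each period receives 4.5λ. Months 12 to 24 add 12(0.5λ) = 6λ. The ratio is (10.5λ/18)/(4.5λ/6) = 0.583/0.75 = 0.78. Spreading the visit over ±2 months and allowing for depletion of men at risk raises it further.

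**Simulation at 0.05 per person-year** (ratio = intervention rate / run-in rate):

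| Routine tests | Kits | True ratio | Mid-point reads |
|---|---|---|---|
| Annual from inclusion | none | 1.0 | 1.16 |
| Annual from inclusion | none | 0.5 | about 0.87 |
| Annual, random phase | none | 0.5 | about 0.61 |
| Annual from inclusion | four, uniform | 1.0 | 0.69 |
| Annual, random phase | four, uniform | 1.0 | about 0.87 |
| Annual from inclusion | between visits (about months 9, 15, 21) | 1.0 | 0.57 |
| Annual, random phase | between visits | 1.0 | 0.74 |
| Annual, random phase | at the reminders | 1.0 | 1.03 |
| Six-monthly, random phase | none | 0.5 | 0.55 |

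**Across 0.033 and 0.203 per person-year.** Annual tests near months 12 and 24 read 0.87 to 0.92 for a true 0.5. Annual tests plus kits between visits read 0.56 to 0.57 under no effect (0.74 to 0.76 at random phase). Three-monthly testing reads 0.97 to 1.01 for a true 1 and 0.50 to 0.53 for a true 0.5. Six-monthly tests aligned with the questionnaires show no bias. Enzyme-triggered testing without kits (run at 0.10 per person-year) reads 0.58 to 0.61 under no effect.

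**Interval-censored likelihood on the same tests.** An event contributes S(last negative) − S(first positive) and a man without an event contributes S(last negative). Here S(t) = exp[−λ₁·min(t, τ) − λ₂·max(t − τ, 0)] and τ is his randomisation date. In the main illustration it returns 0.98 to 1.04 for a true 1 and 0.49 to 0.52 for a true 0.5.

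**Size at 78 per arm.** Expected events are about 1.3 in the run-in and 3.7 in the intervention period at 0.033, and 7.5 and 18.5 at 0.203. With no effect, annual tests near month 12 and kits between visits, the chance of a falsely significant reduction (one-sided 0.025) is 5% at the low rate and 22% at the high rate. With random-phase annual tests it is 2% and 6%. With tests at month 6 it is about 1 to 1.5%.

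**The case against.** **The direction is not fixed.** A reader might infer that sparse testing always hides a true reduction and that home kits always create a false one. The documents do not support that. Enzyme-triggered testing is also sparse, yet it manufactures a reduction, in arm I too. Annual tests with kits used at the month-12 and month-18 reminders read 0.99 to 1.24 under no effect, so no false reduction appears. This objection stands in full.

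**The largest figures need particular schedules.** They require a negative test at month 0 and annual testing anchored to inclusion, and the plan specifies neither. Men tested every 3 to 6 months contribute little bias. This also stands: the figures illustrate and do not predict.

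**The remedy costs precision.** At 0.05 per person-year, 78 per arm and no effect, the standard error of the log rate ratio rises as follows:
- annual from inclusion: 0.87 to 1.49 (+71%);
- the same with four kits: 0.78 to 1.11 (+42%);
- annual at random phase: 0.84 to 1.10 (+31%);
- six-monthly at random phase: 0.83 to 0.95 (+14%).

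For annual tests with four kits, the bias is ln 0.69 = −0.37. Mid-point dating then has mean squared error 0.37² + 0.78² = 0.75 against 1.11² = 1.23, so it wins on that criterion in a single arm at this rate. The arithmetic is right, and it is a good reason to report both analyses. It does not rescue mid-point dating as the main one: its narrower interval treats unknown dates as known, and its centre moves with the testing schedule.

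**The consequence is limited.** The endpoint is secondary, few events are expected, and the SAP specifies a between-arm contrast for the HCV-MOSAIC score (3.5.5) but not for reinfection. This stands, although the by-arm ratios will still be read side by side.

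**Conclusion.** The concern holds in this form: as written, the plan lets test timing help decide the period of an event, so the reinfection rate ratio carries a schedule-dependent bias of either sign that can differ between arm I and arms II/III. Under annual testing it can be large on the ratio scale: no effect reads anywhere from 0.57 to 1.16, and a true 0.5 without kits reads 0.61 to 0.87. With six-monthly or more frequent testing it is small, mainly a mild dilution of a true effect.

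These sizes rest on an assumed rate of 5 per 100 person-years, a negative test at month 0, and assumed timing of visits and kits. They are frequentist rate ratios; a weakly informative Bayesian model fed the same mid-dates inherits the same misplacement. The documents do not support reading this as a flaw in the primary endpoint or the sample size, or as showing that the arms will in fact look different. The change is worth making because it is inexpensive, not because the trial's main conclusion depends on it.

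**What to change.** In SAP 2.3.2, retain the last-negative and first-positive dates for each case and state how the lower limit is set when the last negative test predates inclusion. In 2.2.2, fit the planned Bayesian exponential model with the interval-censored likelihood shown above, with the hazard changing at each man's own randomisation date. Report mid-point dating alongside as a sensitivity analysis, with a tie rule for mid-dates that fall on randomisation. Report by arm the number of events whose test gap straddles randomisation.

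The cost is SAP wording and a few lines of model code; Protocol 11.1 already provides for collecting RNA test dates and results. Intervals will be noticeably wider, by about 14% with six-monthly and up to about 70% with annual testing, largely because uncertainty about dates is now counted.

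The limits should be stated in the SAP:
- The method cannot recover the period when months 0 and 24 are the only tests. In that case it returned 3.3 for a true 1 and 1.4 for a true 0.5.
- It does not fully remove informative timing, such as exposure-driven kit use or enzyme-triggered tests, and it was not checked for the enzyme-triggered schedule.
- Self-reported cases need bracketing test dates, or a stated rule where these are missing.
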